Identification number, gender, year of birth or age at the start of Nucala administration, start date of Nucala administration, presence and absence of obtained informed consent regarding study result publication, body weight, reasons for use of Nucala, date (month, year) of EGPA diagnosis, severity classification of EGPA^{*1} at the start of Nucala administration, presence or absence of hospitalization due to EGPA in 48 weeks before the start of Nucala administration and number of times patient experienced hospitalization, presence and absence of past

medical history/comorbidity (bronchial asthma, renal impairment, hepatic function abnormal, others) and name of disease, presence or absence of history of Nucala use for bronchial asthma if a patient has comorbid bronchial asthma.

To protect the confidentiality regarding identification of an individual patient, the identification number should be a unique number assigned to an individual patient by the investigator, etc.

In this study, any disease, symptom, and allergy history other than EGPA which is present before the start of administration of Nucala but has recovered/resolved by the start of Nucala administration will be handled as a “past history”. Meanwhile, any disease, symptom, and allergy other than EGPA which is present at the start of Nucala administration will be handled as a “comorbidity”.

*1 : Severity Classification of EGPA defined by Japan Intractable Diseases Information Center (Japan Intractable Diseases Research Foundation)

3. Administration status of Nucala
Single dose during the observation period (mg/dose), daily dose frequency (X times per day), administration date, reasons for revision of dosage and administration
4. Pre-treatment medications (during 4 weeks before the start of Nucala administration) and concomitant medications (adrenal cortical steroid (including medications for bronchial asthma), immune-suppressive agent and immunoglobulin preparations only)
Presence or absence of adrenal cortical steroid (including medications for bronchial asthma), immune-suppressive agent and immunoglobulin preparations during 4 weeks before the start of Nucala administration and during the observation period, name of drugs, daily dose, start date of administration, end date of administration, reasons for administration
5. Concomitant medications (other than adrenal cortical steroid, immune-suppressive agent and immunoglobulin preparations)

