 - iii). Number of patients included in the analysis sets regarding remission and recurrence, number of patients excluded from the analysis sets and the reason for exclusion
 - 2) Safety-related matters
 - i). Occurrence of ADRs/infections (type, severity and incidence of ADRs, etc.)

- ii). Factors that potentially affect safety (occurrence of ADRs and infections by patient characteristics, etc.)
 - iii). Occurrence of events defined as a priority study matters
- 3) Effectiveness-related matters
 - i). Responder rate based on global assessment of effectiveness
The responder rate is the proportion of patients assessed as “effective”.
 - ii). Factors that potentially affect effectiveness (responder rate by patient characteristics, etc.)
 - iii). Time to EGPA remission and recurrence
The remission and recurrence are defined as follows;
 - Remission: BVAS=0 in the assessment of disease activity in systemic vasculitis assessed by 9 organ-system, 51 items.
 - Recurrence: If any of the following occurs during the observation period
 - Initiation/increased dose of adrenal cortical steroid
 - Initiation/increased dose of immune-suppressive agent
 - Hospitalization in association with the EGPA treatment
- 2. Analysis methods
Concerning the items associated with safety and effectiveness, etc., the odds ratio and 95% confidence interval will be calculated for factors that potentially affect them. These will be graphically presented using a forest plot, etc., as appropriate. For comparison of the scores, etc., the mean values and quartile points, etc. for values at the time of measurement and changes from baseline will be calculated.

10. Organizational Structure

Refer to the Attachment 1.

11. Name, Address of the Outsourcees, and the Scope of Outsourced Operations

CCI

12. Scheduled Timing to Be a Milestone for Assessing the Status and Results in the Study or Reporting to the Pharmaceuticals and Medical Devices Agency (PMDA) and Rationale

- At the time of Periodic Safety Reports: consideration will be comprehensively given to the safety and effectiveness information.
- At the time of re-examination application: the final report will be prepared/submitted, based on the results of tabular analysis obtained from the fixed data of all collected CRFs.

13. Additional Measures that Have a Potential to Be Taken Depending to the Study Results and the Decision Criteria for the Start

The RMP, including the following, will be reviewed at the timings to be a milestone.

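### The steroid and immunosuppressant criteria for EGPA recurrence have no indication limit, so drug changes for asthma or other non-EGPA reasons count as recurrence when read as written

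*Combined protocol and SAP*

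**What the plan says.** Section 9, item 1.3 iii, lists time to EGPA remission and recurrence among the effectiveness analyses. The rule opens "Recurrence: If any of the following occurs during the observation period" and gives three criteria: "Initiation/increased dose of adrenal cortical steroid", "Initiation/increased dose of immune-suppressive agent" and "Hospitalization in association with the EGPA treatment". Only the third mentions EGPA.

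The drug data come from Section 8 item 4, which records "Presence or absence of adrenal cortical steroid (including medications for bronchial asthma), immune-suppressive agent and immunoglobulin preparations" in the 4 weeks before the start of Nucala and during the observation period. For each it records "name of drugs, daily dose, start date of administration, end date of administration, reasons for administration".

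Section 8 item 2 lists bronchial asthma under past history and comorbidity. The rule there is that "any disease, symptom, and allergy other than EGPA which is present at the start of Nucala administration will be handled as a" comorbidity. Section 8 item 11 separately collects the frequency of asthma exacerbations, including those that need systemic steroids. Section 8 item 12 collects dated hospitalizations for EGPA treatment.

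**The concern.** The outcome is named as EGPA recurrence, but two of its three criteria are treatment changes with no stated indication. The source of the steroid data expressly covers asthma medication. An analyst who follows the text would therefore count a steroid course for an asthma exacerbation, or one given for an unrelated condition, as an EGPA recurrence. The same asthma course may also be counted under the separate asthma item.

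Recurrence is one of the few effectiveness results the plan lists, and no comparator group is described. The absolute proportion and the time to event are therefore the result, and no contrast exists in which extra events could cancel. Under Sections 12 and 14 the results go to the regulator, to clinical sites and to publication.

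**Working it through.** **Reading the passages side by side**

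1. *Combination rule.* Any single criterion is enough, at any time in the observation period (Section 9, item 1.3 iii). A non-EGPA drug change needs no supporting EGPA finding to count.
2. *Indication.* The hospitalization criterion is limited to EGPA treatment. The steroid and immunosuppressant criteria are not limited by indication, route, size of increase or duration.
3. *Data source.* Section 8 item 4 includes steroids for asthma. It records reasons for administration, but Section 9 does not use that field.
4. *Status of asthma.* Section 8 item 2 handles asthma as a condition other than EGPA, so in the protocol's own terms steroid given for asthma is not EGPA treatment.
5. *Limits applied elsewhere.* For asthma exacerbations, Section 8 item 11 specifies systemic use, a minimum of three days and, for patients on maintenance steroid, a doubling of dose. None of these limits is carried into the recurrence rule.

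Nothing in the visible text adds an indication limit to the two drug criteria.

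**Direction**

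Every event that meets an EGPA-attributed rule also meets the unrestricted rule. The counted proportion can therefore only be equal or higher, and the time to first event only equal or shorter.

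**Size, by illustration only**

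The documents give no recurrence rate, no rate of steroid use and no sample-size calculation for recurrence, so there is no plan figure to reproduce. Assumed inputs, none from the documents:

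- non-EGPA starts or increases at a constant rate r of 0.1 to 0.5 per patient-year;
- EGPA-attributed recurrence of 30% at 96 weeks;
- independence of the two kinds of event;
- full follow-up of 96 / 52.18 = 1.84 years.

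P = 1 − exp(−r × 96 / 52.18), and counted recurrence = 1 − (1 − 0.30)(1 − P).

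| r per year | P (at least one non-EGPA event) | Counted recurrence | Excess over 30% |
|---|---|---|---|
| 0.1 | 16.8% | 41.8% | 11.8 points |
| 0.3 | 42.4% | 59.7% | 29.7 points |
| 0.5 | 60.1% | 72.1% | 42.1 points |

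The inflation is the last column, not P.

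Independence matters. If the two kinds of event overlapped as far as possible in the same patients, the counted proportion would be the larger of 30% and P: 30%, 42.4% and 60.1% for the three rates.

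A second set of assumptions uses constant hazards per 48 weeks, *a* for EGPA-related and *b* for non-EGPA events, over two such periods. The EGPA-only proportion is 1 − exp(−2a), the counted proportion is 1 − exp(−2(a + b)), and the non-EGPA share of first events is b / (a + b). For b from 0.1 to 0.4:

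| a | EGPA only | Counted | Non-EGPA share of first events |
|---|---|---|---|
| 0.1 | 18.1% | 33.0% to 63.2% | 50% to 80% |
| 0.2 | 33.0% | 45.1% to 69.9% | 33% to 67% |
| 0.3 | 45.1% | 55.1% to 75.3% | 25% to 57% |

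Both sets show how strongly the answer depends on inputs that the documents do not supply.

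**The case against.** **The absence of a limit is not a statement that any reason counts.** The item is headed as EGPA recurrence, reasons for administration are collected, and Section 9 item 1.1 iii provides for exclusions from the remission and recurrence analysis sets. The Implementation Guidance and case report forms are listed in Section 16 but not reproduced, and they might tie drug changes to EGPA. This stands as a caution: the finding is about the rule as written. It does not remove the finding, because limiting one criterion of three in words makes the literal reading of the other two the natural one.

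**A broad collection field is not an event definition.** This also stands. A reader might infer that every new asthma steroid product, inhaled included, is certain to be scored as a recurrence. Section 8 item 4 sets what is recorded. The recurrence rule fails to exclude such products, but that is not a decision to count them.

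**A broad rule may be deliberate, and asthma and EGPA are hard to separate.** The disease-activity items include the chest and ENT systems, so worsening labelled as asthma may be EGPA activity. This is a good reason to keep the any-reason result in view, but not to report it alone under an EGPA label.

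**The contrast with hospitalization has a practical explanation.** Section 8 item 12 dates only hospitalizations for EGPA treatment, and an asthma admission with a steroid start would still count through the steroid criterion. This weakens the contrast as evidence of contradictory results. The three criteria still differ in what they attribute to EGPA.

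**The size rests on assumptions.** Conceded. Observation ends at withdrawal (Section 6), so full follow-up is optimistic, and overlap between asthma and EGPA worsening would shrink the excess.

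**Conclusion.** The point holds for the rule as written. The drug criteria admit non-EGPA treatment changes as EGPA recurrence, and the direction relative to an EGPA-attributed definition is certain. The size cannot be determined from the documents. The move from 30% to about 42% to 72% rests wholly on the assumed rates, independence and full 96-week follow-up.

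Two stronger readings are tempting, but the documents do not support them.

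- A reader might infer that the plan overstates true relapse. The definition also leaves out worsening of disease activity without a treatment change or an EGPA admission, so the net error against true relapse is unknown.
- A reader might infer that asthma severity is bound to emerge as a recurrence factor. The only factor analysis that Section 9 names for effectiveness is responder rate by patient characteristics, and the general sentence on odds ratios does not mention recurrence.

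This should be fixed, but it is not critical. Recurrence is a descriptive item in a post-marketing investigation whose sample size rests on serious infection, and the data for at least a partial separation are already collected.

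**What to change.** Reconcile the three criteria in Section 9, item 1.3 iii:

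- Analyse time to recurrence with a steroid or immunosuppressant start or increase counted only when the reason recorded under Section 8 item 4 is EGPA.
- Report the any-reason definition beside it as a sensitivity analysis.
- Infer systemic use from the drug name where possible, because route is not among the listed items.
- Flag dose increases that cannot be attributed, and analyse them both as events and as non-events. Section 8 item 4 does not list a reason for each increase, whereas Section 8 item 3 records reasons for changes to Nucala dosing.

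The asthma item cannot do this work, because it collects exacerbation frequency and not the date of each course.

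The cost is a short amendment to the definition, a review of the reason field and one extra analysis. No new data item is needed, but the separation will be only partial. Section 15 item 1 requires advance notification to the regulator unless the change is minor. Final analysis was scheduled for completion in July 2025. If recurrence results already exist, present the attributed analysis as a stated correction.

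The downside is that some asthma-labelled worsening may be EGPA activity and some increases will stay unattributable. The paired analyses show how much this matters.

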It also covers patients who had been registered to a special drug use investigation, SDUI (Protocol No.204524) for bronchial asthma, but had a change in treatment purpose from bronchial asthma to EGPA during the observation period.

* : Irrespective of whether patients have a history of Nucala treatment for bronchial asthma or not

4. Target Sample Size and Rationale

Target number of patients: 300 patients (as a safety analysis population)

Rationale:

In a phase III international joint study conducted in EGPA patients (mepolizumab group: 68 patients), the incidence of serious infection defined as the important potential risk was 5.88% (4/68 patients). On the assumption that the incidence used as a threshold is 6%, to confirm that the lower bound of the two-sided 95% CI exceeds the 6% threshold when the real risk exists two times or more, 277 patients are required as a safety analysis population. Accordingly, the target number of patients was set at 300 in consideration of the dropouts.

5. Planned Number of Medical Institutions by Department

All medical institutions where Nucala is administered to EGPA patients

6. Study Period

1. Study conduct

Study period: from the approval of EGPA indication to three months after termination of the observation period in patients eligible for case report form (CRF) collection (period of the follow-up investigation, if conducted) or the lifting of approval conditions, whichever comes later

Observation period: The observation period per patient is up to 96 weeks (2 years) from the start of Nucala administration for EGPA at a maximum. If a patient has withdrawn from/terminated administration of Nucala, it will be until the withdrawal/termination. Additionally, to consider the safety and effectiveness of Nucala administration in patients who had withdrawn from/terminated due to “symptom improvement”, the 48-week (1-year) follow-up investigation should be conducted as much as possible.

Scheduled enrolment period: from the approval of EGPA indication to the lifting of approval condition

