Continuation status of Nucala at Weeks 12, 48 after the start of administration, end of the observation period, the reason if a patient has withdrawn from/terminated administration
15. Pregnancy
Whether Nucala is administered to a pregnant woman or not, the presence or absence of pregnancy during the observation period, and the expected delivery date (if a patient is female)
In addition, the follow-up investigation should be conducted for a mother and her foetus as far as possible regarding the course of delivery, spontaneous abortion, elective abortion, and AEs, etc.
16. Adverse events (AEs)
Presence or absence of AEs after the start of Nucala administration, diagnosis or symptoms, occurrence date, outcome of AEs, outcome date, seriousness, reason for assessing as serious, relationship to Nucala, factors suspected of being related to AEs other than Nucala
 - 1) In this study, the safety specifications matters are defined as follows;
 - Hypersensitivity including Anaphylaxis, Infections, Malignant tumor
 - 2) To grasp the safety specifications and ADRs, the investigator will collect the information about all AEs (e.g., a disease, symptom, abnormal laboratory value) occurring after the start of Nucala administration on the CRF, regardless of whether or not Nucala is related to an AE. Considering whether or not the possibility of a reasonable relationship to Nucala is present, etc., the relationship to Nucala will be assessed on any of “related” or “not related”.
 - 3) The AEs assessed as “related” to Nucala will be handled as an “ADR” suspected of being caused by Nucala.
17. Follow-up investigation (only in patient who has withdrawn from/terminated due to “symptom improvement”)
Assessment date after the end of follow-up period, presence or absence of AEs leading to death, serious infections, PML, and MT, diagnosis or symptoms, occurrence date, outcome of AEs, outcome date, seriousness, reasons for assessing as serious, relationship to Nucala, factors suspected of being related to AEs except Nucala

9. Analysis Items and Methods

1. Analysis items
 - 1) Patient disposition-related matters
 - i). Number of enrolled patients and number of patients whose CRF is collected and fixed
 - ii). Number of patients included in the safety analysis set and number of patients included in the effectiveness analysis set, number of patients excluded from analysis and the reason for exclusion

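### Section 9.2 names only odds ratios for factor analyses although time at risk differs between patients, so crude ratios for ADRs and infections may be biased upward for factors linked to longer treatment; no method is stated for the two time-to-event outcomes.

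*Combined protocol and SAP*

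**What the plan says.** Section 9.2 of the protocol covers safety and effectiveness items together and names one measure of association for factors: "the odds ratio and 95% confidence interval will be calculated for factors that potentially affect them", shown in a forest plot where suitable. Its only other summaries are means and quartiles for scores and their changes from baseline.

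The factor items in Section 9.1 are both yes/no outcomes: for safety "occurrence of ADRs and infections by patient characteristics, etc", and for effectiveness "responder rate by patient characteristics, etc". Section 9.1 also lists "Time to EGPA remission and recurrence" as an analysis item.

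Section 6 sets the time at risk: "The observation period per patient is up to 96 weeks (2 years) from the start of Nucala administration for EGPA at a maximum". It adds: "If a patient has withdrawn from/terminated administration of Nucala, it will be until the withdrawal/termination". There is one exception. For patients who stop because symptoms improved, "the 48-week (1-year) follow-up investigation should be conducted as much as possible". Section 8, item 17 limits the events asked about in that follow-up to "presence or absence of AEs leading to death, serious infections, PML, and MT".

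The documents contain no person-time rate, exposure adjustment, censoring rule or time-to-event method.

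**The concern.** The study's purpose is long-term safety and effectiveness. Infections and malignancy, two of its three safety specifications, can arise at any time during exposure. An odds ratio for ever having an event counts an event-free patient seen for 8 weeks the same as one seen for 96 weeks. If a characteristic is associated with staying on treatment, patients who have it get more time in which an event can be recorded. Their odds of an event then rise even if their rate does not.

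The factor tables inform the risk management plan review in Section 13. A factor could be flagged, or its apparent protection weakened, because of retention alone.

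For time to remission and recurrence the issue is separate. Patients who withdraw, or reach Week 96 without the event, have censored times. Means and quartiles of observed times do not handle these, and the plan does not say what will.

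**Working it through.** **The plan's own figure.** Section 4 asks for 277 patients so that the lower bound of a two-sided 95% CI exceeds 6% when the true risk is at least doubled (12%). No power is stated. With 95% power the score formula gives ((1.960·√(0.06·0.94) + 1.645·√(0.12·0.88))/0.06)² = ((0.4655 + 0.5345)/0.06)² = 277.8. Exact power with Wilson limits is 95.2% at n = 277. So the figure reproduces if 95% power was meant, and it does not depend on the present point. Section 4 also shows that incidence there means a simple proportion of patients (4/68), so the word in Section 9.1 does not imply a person-time rate.

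**Inputs.** Maximum observation is 96 weeks, ending at withdrawal (Section 6). Everything else is assumed: constant event hazard λ, independent constant withdrawal hazard μ, and no effect of the factor on λ. Time is scaled so that 96 weeks = 1. The full-follow-up risks of 6% and 12% match Section 4; 30% and 60% stand for commoner outcomes. Withdrawal by Week 96 is 20% in the group with the factor and 40% or 60% in the group without it.

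**Formulas.** λ = −ln(1 − risk); μ = −ln(1 − withdrawal). Observed proportion with an event: p = λ/(λ+μ) · (1 − e^−(λ+μ)). Mean time at risk = p/λ, so events divided by person-time equal λ in each group and the rate ratio is 1.00.

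**Worked case, 12% risk, 20% versus 60% withdrawal.**
- λ = 0.1278; μ = 0.2231 and 0.9163.
- p = 0.1278/0.3509 · (1 − 0.704) = 0.1078, and 0.1278/1.0441 · (1 − 0.352) = 0.0793.
- Odds ratio = (0.1078/0.8922)/(0.0793/0.9207) = 1.402.
- Mean time at risk is 81.0 and 59.6 weeks.

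| Full-follow-up risk | p at 20% withdrawal | p at 40% | p at 60% | OR, 20% vs 40% | OR, 20% vs 60% | Rate ratio |
|---|---|---|---|---|---|---|
| 6% | 5.38% | 4.71% | 3.95% | 1.151 | 1.385 | 1.00 |
| 12% | 10.78% | 9.45% | 7.93% | 1.158 | 1.402 | 1.00 |
| 30% | 27.07% | 23.85% | 20.17% | 1.185 | 1.468 | 1.00 |
| 60% | 54.68% | 48.80% | 42.00% | 1.266 | 1.666 | 1.00 |

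**False signals.** With 150 patients per group, the chance that the 95% CI for the odds ratio lies wholly above 1 (nominally 2.5%) was obtained from these proportions. It is roughly 5% at 12% risk with 20% versus 40% withdrawal, 12% at 12% risk with 20% versus 60%, and just under 60% at 60% risk with 20% versus 60%.

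**Early events.** If all risk falls in the first 12 weeks, the event hazard is λ/0.125 and the formula is applied over 0.125 of the period. At 6% and 12% risk the odds ratio is 1.02 (20% versus 40%) to 1.05 (20% versus 60%). At 60% risk it is 1.04 to 1.09.

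**The 48-week follow-up.** Let a share s of withdrawn patients be followed for half of 96 weeks at the same hazard. This adds s · μ/(λ+μ) · (1 − e^−(λ+μ)) · (1 − e^−λ/2) to p. At 6% risk and 20% versus 60% withdrawal, the odds ratio is 1.385 for s = 0, 1.185 for s = 0.5 and 1.046 for s = 1.

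**A truly protective factor.** With a hazard ratio of 0.7 at 12% risk, the odds ratio is 0.80 (20% versus 40%) or 0.97 (20% versus 60%). It is pulled towards 1 but not reversed.

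**Remission and recurrence.** Section 9.1 names the times to these events. Setting that beside Section 9.2 yields no estimator, censoring rule or competing-event rule for them.

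**The case against.** Several objections are sound and limit the point.

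- **Direction and size are not certain.** A reader might infer that every factor linked to longer treatment will look harmful. The calculations do not show that: the bias is small for early events or modest withdrawal differences, and a protective factor can still show an odds ratio below 1.
- **Much larger distortions need extreme retention.** At 6 events per 100 patient-years, mean exposure of 96 versus 48 weeks gives proportions of 10.5% and 5.4% and an odds ratio of 2.06. But a mean of 96 weeks requires that nobody in that group withdraws, and under a constant withdrawal hazard a mean of 48 weeks implies about 80% withdrawal. Nothing in the documents supports that contrast.
- **Early stopping need not look protective.** A patient who stops because of an ADR is counted as having it, so a factor that causes intolerance tends to raise the odds ratio for that ADR.
- **Follow-up does not always end at withdrawal.** The 48-week follow-up reduces the bias for fatal AEs, serious infections, PML and malignancy. It applies only after stopping for symptom improvement, only where possible, and not to other ADRs, remission or recurrence. It also makes observation time depend on the reason for stopping.
- **Odds ratios for remission and recurrence are not stated.** Nor does the plan say that early withdrawals count as failures; it foresees separate analysis sets for these outcomes. A hazard ratio of 2.0 appearing as an odds ratio of 3.0 at equal follow-up (75% versus 50%) is a difference of scale, not bias.
- **The responder rate is not the main target.** It is also rated at withdrawal, so this mechanism does not apply to it in the same way.
- **The link to the package insert is narrow.** Section 13 ties its revision expressly only to hypersensitivity, and there it does consider when events occur.

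What remains is that the only stated association measure ignores time at risk, and that no method is given for two named time-to-event outcomes.

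**Conclusion.** The point holds in this limited form. Crude odds ratios for ADRs and infections may be biased upward for factors linked to longer treatment. Over the assumed scenarios the null odds ratio is about 1.15 to 1.67 against a rate ratio of 1.00. These figures rest on constant hazards, independent withdrawal and assumed withdrawal rates, because the documents give none. They are upper figures for the events that the 48-week follow-up covers.

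For time to remission and recurrence the defect is an unstated method, not a wrong one. The change should be made, but the documents do not support saying that the planned factor results will point the wrong way.

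**What to change.** Amend Section 9.2 as follows.

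- **ADRs, infections and the safety specifications:** report events per 100 patient-years, with rate ratios by factor (Poisson with log-exposure offset) or Cox hazard ratios, beside or instead of the odds ratios in the forest plots.
- **Follow-up period:** state whether its events and person-time count in the main analysis or are shown separately, given the restricted event list and the selected patients.
- **Time to remission and recurrence:** use Kaplan-Meier and Cox, censor at withdrawal or Week 96, and treat death as a competing event. State the assumption that withdrawal is non-informative and add a sensitivity analysis by reason for withdrawal. Withdrawal should not itself be the competing event, because the Week 96 cumulative incidence would then largely reproduce the crude proportion.
- **Global rating:** keep odds ratios at fixed times.

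No new data are needed. Section 8 already collects dates of administration, AE onset, symptom assessment, hospitalization and steroid or immunosuppressant use. A withdrawal date is not listed by name, but the last administration date can serve as an endpoint.

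The costs are somewhat more complex tables, reliance on non-informative withdrawal, and a change to protocol text. Under Section 15 that change needs advance notification to the PMDA unless it counts as minor.
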